9.3.2 Exclusion Criteria

1. Prior anticancer treatment within 28 days (or 5 times the half-life, whichever is shorter) or any investigational agent within 30 days prior to the first dose of study drugs. All acute toxicities related to prior treatments must be resolved to Grade ≤ 1 .

2. Subjects must have recovered adequately from any toxicity and/or complications from major surgery prior to starting therapy.
3. Subjects having >1+ proteinuria on urinalysis will undergo 24-hour urine collection for quantitative assessment of proteinuria. Subjects with urine protein ≥ 1 g/24-hour will be ineligible.
4. Gastrointestinal malabsorption, gastrointestinal anastomosis, or any other condition that might affect the absorption of lenvatinib
5. New York Heart Association (NYHA) congestive heart failure of grade II or above, unstable angina, myocardial infarction within the past 6 months, or serious cardiac arrhythmia associated with significant cardiovascular impairment within the past 6 months
6. Prolongation of QTc interval to >480 msec
7. Active hemoptysis (bright red blood of at least 0.5 teaspoon) within 3 weeks prior to the first dose of study drug
8. Active infection (any infection requiring systemic treatment)
9. Subject is known to be positive for Human Immunodeficiency Virus (HIV), Hepatitis B or Hepatitis C
10. Serious nonhealing wound, ulcer, or bone fracture
11. Known intolerance to either of the study drugs (or any of the excipients)
12. History of organ allograft (subject has had an allogenic tissue/solid organ transplant)
13. Biologic response modifiers (eg, granulocyte colony-stimulating factor within 4 weeks before study entry. Chronic erythropoietin therapy is permitted provided that no dose adjustments were made within 2 months before first dose of study treatment.
14. Any medical or other condition which, in the opinion of the investigator, would preclude participation in a clinical study
15. Females who are pregnant or breastfeeding
16. Excluding the primary tumor leading to enrollment in this study, any other active malignancy (except for definitively treated melanoma in-situ, basal or squamous cell carcinoma of the skin, or carcinoma in-situ of the bladder or cervix) within the past 24 months
17. Prior treatment with lenvatinib (no exceptions) or any PD-1, anti-PD-L1, or anti-PD-L2 agent, except:

- the melanoma and NSCLC cohorts, where prior treatment with one anti-PD-1, anti-PD-L1, or anti-PD-L2 agent is allowed.

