9.4.1.1.8 MANAGEMENT OF QT PROLONGATION

Lenvatinib should be withheld in the event of development of QT interval prolongation ≥ 500 msec. Lenvatinib should be resumed at a reduced dose when QTc prolongation is resolved to <480 msec or baseline. Monitor potassium, calcium and magnesium, and replenish as appropriate.

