9.5.1.5.1 ADVERSE EVENTS AND EVENTS ASSOCIATED WITH SPECIAL SITUATIONS

An AE is any untoward medical occurrence in a patient or clinical investigation subject administered an investigational product. An AE does not necessarily have a causal relationship with the medicinal product. For this study, the investigational products are lenvatinib and pembrolizumab.

The criteria for identifying AEs in this study are:

- Any unfavorable and unintended sign (including an abnormal laboratory finding), symptom, or disease temporally associated with the use of an investigational product, whether or not considered related to the investigational product (Note: Every sign or symptom should not be listed as a separate AE if the applicable disease [diagnosis] is being reported as an AE.)
- Any new disease or exacerbation of an existing disease. However, worsening of the primary disease should be captured under efficacy assessments as disease progression rather than as an AE.
- Any deterioration in nonprotocol-required measurements of a laboratory value or other clinical test (eg, ECG or x-ray) that results in symptoms, a change in treatment, or discontinuation of study drug
- Recurrence of an intermittent medical condition (eg, headache) not present pretreatment (Baseline)
- An abnormal laboratory test result should be considered an AE if the identified laboratory abnormality leads to any type of intervention, withdrawal of study drug, or withholding of study drug, whether prescribed in the protocol or not.

All AEs observed during the study will be reported on the CRF. All AEs, regardless of relationship to study drug or procedure, should be collected beginning from the time the subject signs the study ICF and for 30 days after the last dose of study treatment. Subjects who fail screening primarily due to AE(s) must have the AE(s) leading to screen failure reported. SAEs will be collected for 90 days after the last dose or 30 days following the last dose if the subject initiates new anticancer therapy, whichever is earlier. An AE will not be reported on the Adverse Event CRF if other anticancer treatment is started. All SAEs will be reported on the Adverse Event CRF. All deaths will be collected for 30 days following the last dose of study treatment and reported on the Survival CRF.

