Abnormal laboratory values should not be listed as separate AEs if they are considered to be part of the clinical syndrome that is being reported as an AE. It is the responsibility of the investigator to review all laboratory findings in all subjects and determine if they constitute an AE. Medical and scientific judgment should be exercised in deciding whether an isolated laboratory abnormality should be classified as an AE. Any laboratory abnormality considered to constitute an AE should be reported on the Adverse Event CRF.

Abnormal ECG (QTc) results, if not otherwise considered part of a clinical symptom that is being reported as an AE, should be considered an AE if the QTc interval is more than 450 ms

and there is an increase of more than 60 ms from baseline. Any ECG abnormality that the investigator considers as an AE should be reported as such.

Progression of malignant disease (PD) should not be recorded as an AE in studies where it is included as an endpoint for underlying disease. If the progression leads to an untoward medical occurrence (increased pain, pleural effusion, etc), then this medical occurrence should be the AE.

All AEs must be followed for 30 days after the subject's last dose, or until resolution, whichever comes first. All SAEs must be followed to resolution or, if resolution is unlikely, to stabilization.

Every effort must be made by the investigator to categorize each AE according to its severity and its relationship to the study treatment.

Assessing Severity of Adverse Events

Adverse events will be graded on a 5-point scale according to Common Terminology Criteria for Adverse Event (CTCAE v4.03) ([Appendix 3](#)). Investigators will report CTCAE grades for all AEs (for both increasing and decreasing severity).

Assessing Relationship to Study Treatment

Items to be considered when assessing the relationship of an AE to the study treatment are:

- Temporal relationship of the onset of the event to the initiation of the study treatment
- The course of the event, especially the effect of discontinuation of study treatment or reintroduction of study treatment, as applicable
- Whether the event is known to be associated with the study treatment or with other similar treatments
- The presence of risk factors in the study subject known to increase the occurrence of the event
- The presence of nonstudy, treatment-related factors that are known to be associated with the occurrence of the event

Classification of Causality

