5.6.6 Electrocardiograms

Electrocardiogram (ECG) assessments will be performed at screening and at Day 1 of each cycle. Descriptive statistics for electrocardiogram parameters (HR, PR, QRS, QT, QTcB, QTcF and RR) and changes from baseline will be presented by visit. ECG findings (categorized as normal; abnormal, not clinically significant; and abnormal, clinically significant) will be summarized using shift tables. A subject data listing will also be provided.

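### The numeric QTc adverse-event rule is not aligned with the protocol's own 500 ms withholding level, and no ECG table described in the SAP counts subjects by worst QTcF or largest increase

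*Protocol*

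**What the plan says.** **Recording rule (Protocol 9.5.1.5.1).** An abnormal QTc result that is not already part of a reported clinical picture "should be considered an AE if the QTc interval is more than 450 ms". A second condition, which must also hold, is attached to this threshold: "and there is an increase of more than 60 ms from baseline". The next sentence leaves room for judgment: "Any ECG abnormality that the investigator considers as an AE should be reported as such".

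**Entry (Protocol 9.3.2).** The exclusion reads "Prolongation of QTc interval to >480 msec", so 480 ms is the highest eligible value.

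**Action level (Protocol 9.4.1.1.8).** "Lenvatinib should be withheld in the event of development of QT interval prolongation ≥ 500 msec". Treatment resumes at a reduced dose once QTc has recovered.

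**Other AE criteria (Protocol 9.5.1.5.1).** The criterion that names ECGs begins "Any deterioration in nonprotocol-required measurements of a laboratory value or other clinical test", so it does not reach scheduled ECGs, which the Phase 2 schedule (Table 9) requires every cycle. The criterion triggered by withholding study drug is written for laboratory results only.

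**Analysis (SAP 5.6.6).** ECG parameters, including QTcF and its change from baseline, get descriptive statistics by visit. In addition, "ECG findings (categorized as normal; abnormal, not clinically significant; and abnormal, clinically significant) will be summarized using shift tables". A subject listing is also planned. Protocol 9.7.1.8.5 plans summaries of the same kind. Neither document sets QTc categories.

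**The concern.** Protocol 9.5.1.5.6 names QT prolongation as something already seen with lenvatinib, so it is an event the safety tables should capture reliably. Two parts of the plan do not meet.

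First, the value at which the protocol interrupts lenvatinib is not tied to the value at which an AE must be recorded. The protocol treats a laboratory abnormality that leads to withholding as an AE by rule. A scheduled QTc that leads to withholding has no equivalent provision.

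Second, the SAP has no numeric backstop. SAP 5.6.3 tabulates TEAEs leading to dose interruption or reduction, but that table needs a recorded AE. Without one, the dosing data can show a reduction while no AE table shows its cause. Laboratory values get a shift to worst grade (SAP 5.6.4), and LVEF gets a lowest post-baseline value (SAP 5.6.7). QTcF gets no per-subject worst-value summary.

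**Working it through.** There is no stated figure to reproduce. The check applies the rule literally across the eligible range.

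**Inputs.** AE rule: QTc > 450 ms and rise > 60 ms (Protocol 9.5.1.5.1). Highest eligible entry value: 480 ms (9.3.2). Withholding level: 500 ms or more (9.4.1.1.8).

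**Step 1: when does a withholding-level value miss the rule?** Let B be baseline and Q the on-treatment QTc. At Q of 500 ms or more the first condition is always met, so the rule fails exactly when Q − B ≤ 60, that is, when Q ≤ B + 60. The values that trigger withholding but miss the rule are those from 500 to B + 60. This range is non-empty only if B + 60 ≥ 500, which gives B ≥ 440.

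**Step 2: numbers.**

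| Baseline (ms) | Rise at 500 ms | Rule met at 500 ms? | Largest QTc not meeting the rule (B + 60) |
|---|---|---|---|
| 439 | 61 | yes | 499 |
| 440 | 60 | no | 500 |
| 450 | 50 | no | 510 |
| 460 | 40 | no | 520 |
| 470 | 30 | no | 530 |
| 480 | 20 | no | 540 |

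The eligible baselines with a gap are exactly 440 to 480 ms. The gap spans B − 440 ms: nothing beyond the single value 500 at B = 440, where 501 ms already meets the rule, and 40 ms (500 to 540) at B = 480.

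**Step 3: what the SAP would show for such a subject.**

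- *By-visit statistics.* SAP Section 5 includes minimum and maximum, so a scheduled reading of 500 ms sets or lies below the maximum QTcF at that visit. But SAP Section 8 restricts by-visit analyses to scheduled visits. A column of visit maxima does not say how many subjects reached a value, or whether successive maxima belong to the same subject. The largest QTcF and the largest change in a row may also come from different people.
- *Shift table.* SAP Section 8 includes unscheduled assessments here. The categories are overall ECG interpretations, so a subject shifted to clinically significant abnormal is not identified as a QTc case.
- *Listing.* The individual values are there, but not a count.

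**The case against.** The strongest reply is that the numeric rule adds a mandatory trigger and takes nothing away. It says when a result should be an AE; it does not say that nothing else may be. The investigator may report any ECG abnormality, and the first general criterion in 9.5.1.5.1 covers any unfavorable, unintended sign without restriction to unscheduled tests. An investigator who has just withheld lenvatinib could well record the event. An unscheduled ECG that leads to a change in treatment falls under the criterion on non-required measurements. The reason for a dosage change is recorded on the CRF (Protocol 11.5), and dose reductions and interruptions are counted from dosing data (SAP 5.6.1). All of this stands. It means that capture is discretionary; it does not mean that capture is absent.

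A reader might infer that the SAP hides QTc outliers. The documents do not support that: maxima are printed by visit, the shift table includes unscheduled ECGs, and values are listed. What is missing is narrower, namely a count of subjects by threshold. The table shells are a separate document (SAP Section 11) and were not available, so they may go further than the SAP text.

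Timing also matters. The revision history shows that Amendment 09 added the QT management section, while the SAP is based on Amendment 8. The SAP could not have been built around the 500 ms level. The same amendment describes the primary endpoint analysis as completed, so a revised AE rule would reach only subjects still being followed. It would also mix two ascertainment rules in one safety table. This is a good reason to put the weight on the SAP table. It does not remove the mismatch in the current protocol.

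**Conclusion.** The point holds as a misalignment with a modest, unquantified effect. For eligible baselines of 440 to 480 ms, a scheduled QTc of 500 ms or more can trigger withholding without meeting the mandatory AE rule, and no ECG table described in the SAP counts such subjects. QT events may be under-recorded as a result.

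Three stronger readings go beyond the documents:

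- *That these events will go unrecorded.* The rule leaves recording to judgment; it does not forbid it.
- *That the combination's QT incidence is understated.* No baseline or on-treatment QTc distribution is given, so neither the direction nor the size of any error is shown.
- *That every subject entering at 440 to 480 ms is affected.* Only those who reach at least 500 ms while staying within 60 ms of baseline are affected.

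The working assumes that baseline equals the QTc at entry and that the 500 ms level refers to QTc. Section 9.4.1.1.8 speaks of the QT interval for withholding and of QTc for resumption; 9.5.1.5.6 specifies the Fridericia correction for QTc.

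**What to change.** **1. SAP 5.6.6 (main remedy).** Add one table of subjects by worst post-baseline QTcF and by maximum increase from baseline, using scheduled and unscheduled ECGs. Build the categories on values the protocol already uses: above 450, above 480, and 500 ms or more; increase above 60 ms. Cross-classifying the two would show directly how many subjects reached 500 ms with a rise of 60 ms or less. The table works whether or not an AE was reported, and it covers past as well as future ECGs. The cost is one extra table from data already collected.

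**2. Protocol 9.4.1.1.8 and 9.5.1.5.1.** Reconcile the two sections so that it is clear whether a QTc result that triggers the withholding instruction is to be recorded as an AE. This concerns recording only and implies no view on which threshold is right. The cost is a short amendment. It would apply prospectively, and the report should state the date from which it applied.

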9.5.1.5.2 SERIOUS ADVERSE EVENTS AND EVENTS ASSOCIATED WITH SPECIAL SITUATIONS

A SAE is any untoward medical occurrence that at any dose:

- Results in death
- Is life-threatening (ie, the subject was at immediate risk of death from the AE as it occurred; this does not include an event that, had it occurred in a more severe form or was allowed to continue, might have caused death)
- Requires inpatient hospitalization or prolongation of existing hospitalization
- Results in persistent or significant disability/incapacity
- Is a congenital anomaly/birth defect (in the child of a subject who was exposed to the study drug)

Other important medical events that may not be immediately life-threatening or result in death or hospitalization but, when based on appropriate medical judgment, may jeopardize the subject or may require intervention to prevent one of the outcomes in the definition of SAE listed above should also be considered SAEs. Medical and scientific judgment should be exercised in deciding whether expedited reporting is appropriate in such situations.

Events of clinical interest for this study include:

1. an elevated AST or ALT laboratory value that is greater than or equal to $3 \times$ ULN and an elevated total bilirubin lab value that is greater than or equal to $2 \times$ ULN and, at the same time, an ALP laboratory value that is less than $2 \times$ ULN, as determined by way of protocol-specified laboratory testing or unscheduled laboratory testing.

Note: These criteria are based upon available regulatory guidance documents. The purpose of the criteria is to specify a threshold of abnormal hepatic tests that may require an additional evaluation for an underlying etiology. The study site guidance for assessment and follow up of these criteria can be found in the Investigator Trial File Binder (or equivalent). It may also be appropriate to conduct additional evaluation for an underlying etiology in the setting of abnormalities of liver blood tests including AST, ALT, bilirubin, and ALP that do not meet the criteria noted above. In these cases, the decision to proceed with additional evaluation will be made through consultation between the study investigators and the Sponsor Clinical Director. However, abnormalities of liver blood tests that do not meet the criteria noted above are not events of clinical interest for this trial.

In addition to the above, events associated with special situations include pregnancy or exposure to study drug through breastfeeding; and AEs associated with study drug overdose, misuse, abuse, or medication error. These events associated with special situations are to be captured using the SAE procedures but are to be considered as SAEs only if they meet one of the above criteria. All AEs associated with special situations are to be reported on the CRF whether or not they meet the criteria for SAEs.

All SAEs must be followed to resolution or, if resolution is unlikely, to stabilization.

The following hospitalizations are not considered to be SAEs because there is no AE (ie, there is no untoward medical occurrence) associated with the hospitalization:

- Hospitalizations for respite care
- Planned hospitalizations required by the protocol
- Hospitalization planned before informed consent (where the condition requiring the hospitalization has not changed after study drug administration)
- Hospitalization for administration of study drug or insertion of access for administration of study drug
- Hospitalization for routine maintenance of a device (eg, battery replacement) that was in place before study entry

If possible, a blood sample for the measurement of study drug plasma concentration should be drawn at the first report of an SAE or a severe unexpected AE and at its resolution.

9.5.1.5.3 LABORATORY MEASUREMENTS

Clinical laboratory tests to be performed, including hematology, chemistry, and urinalysis, are summarized in Table 7. Subjects should be in a seated or supine position during blood collection. The Schedule of Procedures/Assessments (Table 8 and Table 9) shows the visits and time points at which blood for clinical laboratory tests and urine for urinalysis will be collected in the study.

Table 7 Clinical Laboratory Tests

Category	Parameters
Hematology	Hematocrit, hemoglobin, platelets, RBC count, and WBC count with differential INR ^b
Clinical Chemistry	
Electrolytes	Bicarbonate, calcium, chloride, magnesium, phosphorus, potassium, sodium
Liver function tests	Alanine aminotransferase, alkaline phosphatase, aspartate aminotransferase, direct bilirubin, total bilirubin
Renal function tests	Blood urea nitrogen, creatinine
Thyroid function tests ^a	TSH and free T4 levels
Other	Albumin, cholesterol, glucose, lactate dehydrogenase, total protein, triglycerides, amylase, lipase
Urinalysis	Glucose, ketones, pH, protein, RBCs, specific gravity

RBC = red blood cell, T4 = thyroxine, WBC = white blood cell, INR, International Normalized Ratio.

a. Thyroid function will be assessed every 2 cycles.

b. Only at screening/baseline and when clinically indicated.

All hematology, blood chemistry (including pregnancy test, as applicable), and urinalysis samples are to be obtained prior to study drug administration and results reviewed prior to administration/dispensing of study drug at the beginning of each treatment cycle.

A laboratory abnormality may meet the criteria to qualify as an AE as described in this protocol (see [Section 9.5.1.5.1](#) and the CRF Completion Guidelines (CCG)). In these instances, the AE corresponding to the laboratory abnormality will be recorded on the Adverse Event CRF.

9.5.1.5.4 VITAL SIGNS AND WEIGHT MEASUREMENTS

Vital sign measurements (ie, systolic and diastolic BP [mmHg], heart rate [beats per minute], respiratory rate [per minute], body temperature [in centigrade]), and weight (kg) will be obtained at the visits designated in the Schedule of Procedures/Assessments ([Table 8](#) and [Table 9](#)) by a validated method. Blood pressure and heart rate will be measured after the subject has been resting for 5 minutes. All BP measurements should be performed on the same arm, preferably by the same person. One BP assessment is defined as the mean value of 3 measurements at least 5 minutes apart.

For subjects with an elevated BP (ie, systolic BP ≥ 140 mm Hg or diastolic BP ≥ 90 mm Hg), confirmation should be obtained by performing two assessments a minimum of 1-hour apart.

Subjects with systolic BP ≥ 160 mm Hg or diastolic BP ≥ 100 mm Hg must have their BP monitored every 2 weeks (on D1 and Day 15 or more frequently, as clinically indicated) until systolic BP has been ≤ 150 mmHg and diastolic BP has been ≤ 95 mmHg for 3 consecutive months. See subsection for management of hypertensive subjects ([Section 9.4.1.1.2](#)).

Height will be measured at the Screening Visit only.

9.5.1.5.5 PHYSICAL EXAMINATIONS

Physical examinations including oral examinations will be performed as designated in the Schedule of Procedures/Assessments ([Table 8](#) and [Table 9](#)). Documentation of the physical and oral examination will be included in the source documentation at the site. Only changes from screening physical or oral examination findings that meet the definition of an AE will be recorded on the Adverse Events CRF.

9.5.1.5.6 ELECTROCARDIOGRAMS

Electrocardiograms will be obtained as designated in the Schedule of Procedures/Assessments ([Table 8](#) and [Table 9](#)). Complete, standardized, 12-lead ECG recordings that permit all 12 leads to be displayed on a single page with an accompanying lead II rhythm strip below the customary 3×4 lead format are to be used. In addition to a rhythm strip, a minimum of 3 full complexes should be recorded from each lead simultaneously. Subjects must be in the recumbent position or sitting for a period of 5 minutes prior to the ECG. The Fridericia correction method for calculating QTc will be used.

An ECG abnormality may meet the criteria of an AE as described in this protocol (see [Section 9.5.1.5.1](#)) and the CCGs. In these instances, the AE corresponding to the ECG abnormality will be recorded on the Adverse Events CRF.

QT prolongation has been seen in some lenvatinib studies. Monitor electrocardiograms every cycle (as specified in the Schedule of Assessments) in patients with congenital long QT syndrome, congestive heart failure, bradyarrhythmias, or those who are taking drugs known to prolong the QT interval, including Class Ia and III antiarrhythmics. Refer to the Lenvatinib package insert.

